8.8 Co-enrolment

Co-enrolment defined as the enrolment of a participant in two or more clinical trials either concurrently or sequentially. Co-enrolment will be permitted with other studies/trials provided that the burden is acceptable to the participants and study office. Co-enrolment should not affect the study outcomes, for example if another study involved immunosupression.

9 OBJECTIVES AND OUTCOME MEASURES

9.1 Aims

The aims of the study are to further establish the impact and safety of SSF use in solid organ transplants; to determine immunological mechanisms of early rejection and combination transplantation, and to identify biomarkers of acute rejection to aid diagnosis of rejection and identify potential therapeutic targets.

9.2 Primary objective and outcome measure

Objective	Outcome measure	Time point(s) of evaluation of this outcome measure (if applicable)	Data required	Source data (including location)
To assess the efficacy of the sentinel skin flap (SSF) at reducing rates of acute lung rejection by 12 months post-transplantation	in the first 12 months, diagnosed	first rejection event in	Date of randomisation; date of first diagnosed lung rejection; date of death (if prior to diagnosis of lung rejection); date of withdrawal (if prior to diagnosis of lung rejection).	Participant's medical notes (clinical diagnosis); Histology report (biopsy diagnosis)

9.3 Secondary objectives and outcome measures

	Objective	Outcome measure	Time point(s) of	Data required	Source data
			evaluation of this		(including location)
			outcome measure		
			(if applicable)		
1.	To compare the	Diagnostic accuracy	Up to 12 months post	Date of first diagnosed	Histology reports
	diagnostic accuracy	(sensitivity,	randomisation	lung rejection; date and	(skin and lung
	of the sentinel skin	specificity, negative		method of first	biopsies)
	flap to the current	predictive value and		diagnosed skin	Participant's medical
	reference standard	positive predictive		rejection.	notes
	(organ biopsy	value) of the sentinel			
	and/or clinical	skin flap compared			
	diagnosis) ²	to current reference			
		standard (biopsy			
		and/or clinical			
		diagnosis) ²			
2.	Safety of sentinel	a. Number and	Up to 12 months post	Date of randomisation;	Participant's medical
	skin flap	severity of skin flap	randomisation	date of first diagnosis of	notes and
	transplantation ²	rejection episodes		skin rejection; date of	

SENTINEL_Protocol_V1.1_27Apr2023.docx IRAS number: 318347 REC Reference: 23/LO/0248

		T	T	1	Ι .
		(defined by biopsy		death (if prior to	Histology reports
		BANFF grade ≥ 1) and		diagnosis of skin	(skin biopsies)
		time to firstrejection		rejection); date of	
		diagnosis ²		withdrawal (if prior to	
				diagnosis of skin	
				rejection); severity of	
				rejection (BANFF grade).	
		b. Transplanted lung	Up to 12 months post	Date of randomisation;	Participant's medical
			randomisation	date of first loss of lung	notes/death record
		'		failure; date of death;	,
				date of withdrawal (if	
				prior to lung loss or	
				death)	
		c. Transplant lung	12 months post	Lung function tests	Participant's medical
		function ¹	randomisation	(spirometry): Vital	notes
				capacity (absolute	liotes
				values and % predicted);	
				Forced expiratory	
				volume (absolute values	
		1.6	11. 1. 42	and % predicted)	De distance de la constance de
		d. Surgical	Up to 12 months post	Surgical complications	Participant's medical
		complications and	randomisation	(flap failure, wound	notes
		complications		healing problems,	
		relating to the SSF		infection, skin necrosis,	
		(such as infection,		nerve injury);	
		skin loss, nerve		Delayed complications	
		injury) ¹		(pain, hand symptoms	
				including paraesthesia,	
				numbness, weakness)	
		e. Development of	Events up to 12	Presence of de-novo	Immunological
		de-novo donor	months post	antibodies	laboratory report
		specific antibodies ¹	randomisation		
		f. Development of	Events up to 12	Diagnosis of graft versus	Participant's medical
		graft versus host	months post	host disease	notes
		disease ¹	randomisation		
		g. Evidence of	12 months post	Chronic rejection	Histology report
		chronic rejection in	randomisation	S. A SING TOJOCKION	
		lung ¹	Tanaomisadon		
3	To establish if the	Immunosuppression	Events up to 12	Number and type of	Prescription for
٥.	addition of a	levels and	months post	immunosuppressants	immunosuppressants
	sentinel skin flap	requirements ¹	randomisation	given and target levels	Immunosuppressants
		requirements	randomisation		
	changes the			/doses (steroid,	
	immunosuppressio			mycophenolate mofetil	
	n requirements			(MMF), tacrolimus,	
_	-		B 11 0 1 1 2	others);	5
4.	To establish if		Baseline, 3 and 12	SF-36; EQ-5D-5L; DAS-24	
	being able to	by the following	months post		outcome measure
	personally check	validated	randomisation		
	on immune	questionnaires: SF-			
	response/rejection	36; EQ-5D-5L and			
	of transplant	DAS-24 ¹			
1					

changes quality of		
life, or if rendering		
the transplant		
visible adversely		
effects QoL		

¹ Outcome assessed in both intervention and comparator;

9.4 Exploratory/mechanistic objectives/outcomes

Ok	pjective	Outcome measure	Time point(s) of evaluation of this outcome measure (if applicable)	Sample type
1.	To identify immune pathways in skin and solid organ transplant (SOT) rejection and compare these to known mechanisms	nCounter HOT (human organ transplant) panel	Up to 12 months post randomisation	Lung and skin punch biopsies
2.	To identify the mechanism of immune-modulation by simultaneous transplant of skin and SOT by exploring passenger leucocytes, suppressor T-cells, dendritic antigen presenting cells, immune diversion or paralysis, immune exhaustion, immune response termination sequences, and lymphocytotoxic antibodies	Gene expression	Up to 12 months post randomisation	Lung and skin punch biopsies
3.	To seek to demonstrate the relative proportions of T-cells of both donor and recipient origin including skin homing of T-reg cells, and the role of these cells in preventing rejection	Digital spatial profiling histology	Up to 12 months post randomisation	Lung and skin punch biopsies
4.	To investigate if serum cell- free DNA level correlates with detected rejection	Cell-free DNA Blood sample (cell free DNA)	Up to 12 months post randomisation	Blood sample
5.	To study the role of the cutaneous and lung microbiome on the immunological response	16sRNA analysis	Up to 12 months post randomisation	Lung and skin punch biopsies and/or skin swabs, sputum/bronchial brushings/ bronchoalveolar lavage

9.5 Use of core outcome sets

There are no core outcome sets applicable for this study.

10 STUDY DESIGN AND SETTING

The SENTINEL study is a multi-centre, open-label, two-arm, parallel design, superiority randomised controlled clinical trial.

² Outcome assessed in intervention arm only.

152 patients (76 in each of two trial arms) will be randomised from 5 sites in the UK. Participants will be randomised to either receive a lung transplant with an accompanying sentinel skin flap (SSF) transplant (intervention arm) or a lung transplant only (control/comparator arm) if an organ becomes available for donation.

A study flow chart is provided in Participant pathway graph at section 14.8 (Transplant pathway following consent).

10.1 Recruiting sites/site types

Participants will be recruited from the 5 specialist NHS cardiothoracic transplant centres who perform lung transplants in England.

10.2 Collection of outcome data and follow-up assessments

Participants will receive communications from the SENTINEL study team to collect outcome data and undergo research specific visits.

Refer to Section 17.3 for full details of outcome data collection and follow-up assessments.

For those who consent to take part in the SENTINEL study. The following information will be recorded on a secure web-based form in the SENTINEL study database system (REDCap) by a member of the local study team to enable follow-up/contact:

• Participant details e.g. Name, Hospital number, address, NHS/CHI number, date of birth, telephone number, mobile number, email address, GP name and GP address.

The GP details are required to allow the central study team to send a letter to the participant's GP informing them of their SENTINEL participation after a transplantation procedure. The email address will enable a copy of the completed consent form to be sent to the participant or at their request a different individual for safekeeping. Depending upon participant preference the email /postal address and/or telephone may be utilised for follow up questionnaires, reminders/text messages and thank you letters. This information always be sent in an anonymised form without direct identifiers. Any confidential information that is sent will be marked confidential and will be encrypted and password protecrted.

After consent (Stage 1) baseline data and Health Related Quality of Life will be collected. Baseline HRQoL questionnaires will either be completed on paper or electronically on a tablet device/computer at the recruiting transplant centre. Patients will be sent HRQoL questionnaires again via e-mail or post (according to participant preference) at 3 months, and at 12 months post-randomisation. Questionnaires may also be completed during clinic visits at these time points if the participant has not already completed these when they come in for their visit.

On a suitable SENTINEL recipient / donor match that includes the offer of lungs and skin being found and flagged by NHSBT to the local SENTINEL Study Point of Contact, the potential recipient will be asked by the local team if they are still happy or not to participate in the study. A further consent is then taken and the participant is then randomised.

10.3 Duration of participant involvement

Participants will be in the study for approximately 12 months from randomisation to last protocol visit.

10.4 Post-trial treatment/care and follow-up

Following a participant's final protocol visit, they will receive standard care. It is expected that most skin flaps will be retained after the 12-month study period. The skin flaps can, however, be removed under local or general anaesthesia at the end of the study period if the participant wishes. Ongoing care for the flaps retained after the study period will be performed by the local transplant team with support from the local plastic surgery team.

Participants will undergo routine clinical follow-up after transplantation, as part of standard care for all lung transplant recipients. The relevant participating transplant centres have standard protocols for the management of patients after lung transplantation. Typically, such patients are reviewed in an outpatient clinic very frequently in the first year: 10-15 times in the first 6 months and then 6 times in the second 6 months (this can be more frequent if problems arise). During these visits, standard clinical investigations performed by the relevant participating centres will be performed. These may include full blood count (FBC), renal function tests (U&Es), liver function tests (LFTs), C reactive protein, immunosuppressant medication levels and donor specific antibodies (DSA). There may also be organ-specific investigations such as spirometry, lung function tests, sputum, radiographs, bronchoscopies, bronchial brushings, bronchoalveolar lavage, and allograft biopsies.

Clinical outcomes of the lung transplant will be collected by local healthcare teams, as required by NHSBT and relevant data will be recorded in the case report forms.

Refer to the STUDY ASSESSMENTS/PROCEDURES section for full details of outcome data collection and follow-up assessments.

10.5 Training

Selection and appointments of plastic surgeons to perform the retrievals and transplantation of the skin flaps will ensure their competency in performing the surgery. The forearm flap design chosen for this study, is an established and well-known technique, in use since since 1980. All plastic surgeons should be competent and familiar with VCA transplantation. Further training regarding the specifics of organ retrieval and transplantation will be taught at the annual NHSBT retrieval masterclass course, designed and delivered by Chief Investigator of the study. Written material is available for guidance regarding the transplant procedure. Training of the specialist nurses for organ donation (SNs) involved in requesting and obtaining consent for organ donation will be undertaken by NHSBT. The material for this training and the standard operating protocol has been agreed with NHSBT. The skin biopsy procedure will be taught to the clinical researchers responsible for this procedure.

No pre-implantation blood samples or biopsies will be taken from the skin flap or lung for the purposes of the SENTINEL study.

All surgeons who are part of the study-specific plastic surgery retrieval and transplant team will receive study-specific training relevant to their role.

10.6 Central review procedures

Not applicable. There are no central review procedures for this study. Where site staff require a second expert opinion of the assessment of the skin rash this will be sought as described in section 16.8 Detecting, diagnosing and managing rejection.

10.7 Health Economics

There are no health economic analyses to be undertaken as part of the trial

10.8 Expected recruitment rate

During the 2019-2020 financial year, a total of 156 lung transplants were carried out across all centres in the UK. We estimate that approximately 75% of patients would meet the eligibility criteria for the trial, and that approximately 30-40% of eligible patients will consent to take part in the trial (which we consider is a conservative but realistic estimate). Therefore, once all sites are open, we expect recruitment of 4-5 patients per month (approximately 1 patient per month/per centre). We anticipate one centre per month, following the study opening to recruitment, with all 5 centres open by month 12 at the latest. Therefore, assuming staggered opening of sites, randomisation of 152 participants should be feasible within the 36-month recruitment period.

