24.2 Sample Size/Power calculations

The anticipated 12-month rejection rates for lungs in the control arm by 12 months is 80%. Published rates vary between 33-100% (43–46) depending on definition and grade of rejection and method of analysis. However, a comprehensive study of regular transbronchial biopsies in 299 lung transplant patients showed a cumulative incidence of rejection (≥grade A1) of 91.7% in the first 12 months and (≥grade A2) of 77.9% (46).

In the SSF intestinal study, we observed a 72% reduction in biopsy-proven acute rejections from the 77% rejection rate in the control arm reducing to 22% in the with skin arm. However, as a more conservative estimate for this study, we consider a relative reduction of a third from 80% to 53.33% (corresponding to an absolute difference of 26.67%) to be clinically meaningful. 128 participants who have had a transplant are required for the analysis to achieve 90% power at a two-sided significance level of 5%. To allow for a 15% loss to follow-up or death by 12 months (76 per trial arm) 152 participants need to have been randomised and transplanted. In total, approximately 254 randomisations will be required to achieve this number and account for participants not proceeding with transplant.

Assessment of the diagnostic accuracy of the SSF compared to the current reference standard (organ biopsy) is a secondary objective of this study, and is undertaken in participants who received an SSF. Assuming approximately 80% specificity, and 90% specificity, based on previous studies, 95% confidence intervals (Wilson method) around the sensitivity, specificity, positive and negative predicted values will have a width of approximately 20-30%, depending on the observed sensitivity, specificity and event rates. A sample size of 64 participants receiving SSF and providing one-year follow-up data, an expected rejection rate of 53%, and anticipated values of 80% and 90% for sensitivity and specificity, respectively, will provide approximately 80% power (at a one-sided 5% significance level) to show that the observed sensitivity and specificity in the study are statistically significantly higher than 60% and 70%, respectively.

Since the proposed mechanistic sub-studies are intended to be hypothesis generating, no formal sample size calculations have been performed.

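### The 4-5 patients per month in section 10.8 does not follow from its inputs, which give 2.9-3.9, and sections 10 and 10.8 count 152 randomised where section 24.2 needs 152 transplanted

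*Protocol*

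**What the plan says.** Section 10.8 builds the recruitment forecast from three inputs. In 2019-2020, "a total of 156 lung transplants were carried out across all centres in the UK". Eligibility is the second input: "approximately 75% of patients would meet the eligibility criteria for the trial". Willingness to join is the third: "approximately 30-40% of eligible patients will consent to take part in the trial". From these it concludes that, once all sites are open, "we expect recruitment of 4-5 patients per month (approximately 1 patient per month/per centre". It plans to open one centre per month, "with all 5 centres open by month 12 at the latest", and ends by saying that "randomisation of 152 participants should be feasible within the 36-month recruitment period".

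The target is worded in several ways:

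- Section 10: "152 patients (76 in each of two trial arms) will be randomised from 5 sites in the UK".
- Section 10.8: again a count of randomised participants.
- Section 6 (synopsis): 152 participants, 76 per arm, without saying whether they are randomised or transplanted.
- Section 5 (lay summary): 152 adults who have a lung transplant.
- Section 24.2: 128 transplanted participants are needed in the analysis for 90% power and, after allowing for 15% loss, "152 participants need to have been randomised and transplanted. In total, approximately 254 randomisations will be required".
- Section 24.9: the intention-to-treat analysis covers patients who were both randomised and transplanted.

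Sections 15.5 and 16.3 return randomised patients who are not transplanted to the waiting list and allow them to be randomised again. Section 17.10 also returns them to the list but adds that they are not replaced.

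**The concern.** The forecast is presented as a consequence of the three inputs, yet the top of the range that they give lies below the bottom of the range stated. The funder, the steering committee and the sites will use that rate to judge whether 36 months is long enough.

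The target has a second problem. A randomised participant and a transplanted participant are different units here: section 24.2 implies that only about 60% of randomisations lead to a transplant. Anyone who decides when to close recruitment from section 10 or 10.8 would work to a different number from someone using section 24.2. At stake are the length of recruitment and, if it is closed on the wrong count or date, the number analysed.

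**Working it through.** **1. The sample size reproduces.** Inputs from section 24.2: 80% versus 53.33%, two-sided 5%, 90% power, 15% loss. With the pooled-variance formula for two proportions and no continuity correction:

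n per arm = [1.96 × √(2 × 0.6667 × 0.3333) + 1.2816 × √(0.80 × 0.20 + 0.5333 × 0.4667)]² / 0.2667² = 63.6, so 64.

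- Total analysed: 2 × 64 = 128, with power 90.2%.
- Inflated for loss: 64 / 0.85 = 75.3, so 76 per arm and 152 in all.
- Randomisations: 152 / 254 = 0.598. A transplant rate of about 60% gives 152 / 0.60 = 253.3, close to the stated 254.

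**2. The monthly rate does not reproduce.** Inputs from section 10.8:

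- Low: 156 × 0.75 × 0.30 = 35.1 a year; / 12 = 2.93 per month.
- High: 156 × 0.75 × 0.40 = 46.8 a year; / 12 = 3.90 per month.

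With the figure of about 200 lung transplants a year given in sections 5 and 8.1, the same formula gives 3.75-5.0 per month, close to the stated 4-5. Section 10.8 does not use that figure.

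**3. What the unit is.** The 156 are completed transplants, so 2.93-3.90 is best read as transplanted participants per month and compared with 152. The 254 should not be applied on top of it.

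**4. Number by month 36, and power if recruitment closed then.** Five sites over 36 months give 180 centre-months.

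- One centre opening per month loses 4 + 3 + 2 + 1 = 10 centre-months, leaving 170, or 34 months at full rate.
- Opening at the start and after months 3, 6, 9 and 12 (an assumed even spread up to the stated latest date) loses 3 + 6 + 9 + 12 = 30, leaving 150, or 30 months at full rate.

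Power is for 80% versus 53.33% after 15% loss.

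| Site opening | Full-rate months | Transplanted | Analysable (× 0.85) | Power |
|---|---|---|---|---|
| All from day 1 | 36 | 105-140 | 90-119 | 77-88% |
| One per month | 34 | 99-133 | 85-113 | 75-86% |
| Spread to month 12 | 30 | 88-117 | 75-99 | 69-82% |

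Every entry is below 152 transplanted. Reaching 152 in 36 months needs 152 / 36 = 4.2 per month with no stagger, or 152 / 34 = 4.5 with one centre per month. At the derived rates it takes 152 / 3.90 = 39 to 152 / 2.93 = 52 months at full rate.

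**5. A separate scenario: stopping at a literal 152 randomisations.** 152 × (152 / 254) = 91 transplanted; 91 × 0.85 = 77 analysable; power about 71%. This reads 152 as raw randomisations and so is an alternative to step 4, not an addition to it.

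**6. Skin donation.** Sections 12.5, 14.1 and 15.1 bar randomisation when the donor offer does not include skin, and section 16.3 says not all families will agree. Section 10.8 states no factor for this, and the protocol gives no rate, so none is applied above.

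**The case against.** A reader might infer that the trial does not deliver its 90% power. The protocol does not support that. The calculation is correct, section 24.2 already asks for 152 transplanted and about 254 randomisations, and section 24.9 defines the analysis set consistently with it. Section 24.17 says recruitment is expected to last 36 months; nothing fixes closure at that date regardless of numbers. The shortfall can be met by recruiting for longer. This stands.

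Other points on that side also stand, in whole or in part:

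- The synopsis does not say randomised, and the lay summary agrees with section 24.2. The conflict in wording is confined to sections 10 and 10.8; section 6 is only unclear.
- If the rate in section 10.8 is read as transplanted patients, its 152 can be read the same way. The 71% then shows the hazard in the wording and is not a consequence of the inputs.
- Because patients can be randomised again, 254 randomisations need not be 254 people. The remark in section 17.10 about not replacing participants could be taken as compounding the loss, but the same sentence puts them back on the list. It needs reconciling, not necessarily deleting.
- Section 12.5 calls recipients of lung-only offers ineligible for randomisation, so skin refusal might already sit inside the 75%. The protocol does not say. One can say only that no factor is stated.

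None of this recovers 4-5 per month from 156 transplants a year.

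**Conclusion.** The point holds in two parts. First, the stated 4-5 per month is wrong on its inputs, which give 2.9-3.9, and 152 in 36 months does not follow under any of the opening patterns examined. This rests on the 156, 75% and 30-40% of section 10.8, on reading the rate as transplanted participants, and on no further loss for skin-donation refusal; any such loss outside the 75% would lower it. Second, sections 10 and 10.8 count randomised participants where section 24.2 counts transplanted ones.

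The consequence is either a longer recruitment period or lower power, depending on what is done at month 36. Closing then would give about 75-86% with one centre opening per month, and 88% at best. Closing at 152 randomisations would give about 71%. The sample-size calculation and the analysis set are unaffected. These figures govern planning and the closing of recruitment, so they should be corrected.

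**What to change.** - **Section 10.8, rate:** replace 4-5 per month with 2.9-3.9 transplanted participants per month. Alternatively, state and justify a different annual figure, such as the 200 in section 8.1.
- **Section 10.8, skin donation:** say whether refusal of skin donation is within the 75%. If it is not, apply an explicit assumed rate and show a range.
- **Section 10.8, conclusion:** restate either the recruitment duration or the number transplanted and the power expected at month 36, with staggered opening allowed for.
- **Sections 10 and 10.8, target:** change it to 152 randomised and transplanted (about 254 randomisations), and clarify section 6 in the same way. Note that the 254 may include repeat randomisations of the same patient.
- **Section 17.10:** reconcile the statement that participants are not replaced with sections 15.5, 16.3 and 24.2.

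The edits are protocol wording only, with no change to the design, the analysis or the sample-size calculation. The cost is a less favourable stated rate on the present inputs and, with it, a longer recruitment period or a lower expected power at month 36.
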